#### **9.4.2 Non-Serious Adverse Events**

The recording of non-serious AEs will begin after the patient signs the informed consent form and will stop at the end of the patient's Follow-up Period. The Investigator will monitor each patient closely and record all observed or volunteered AEs on the Adverse Event Case Report Form.

#### **9.4.3 Evaluation of Adverse Events (Serious and Non-Serious)**

The Investigator's opinion of the following should be documented on the Adverse Event Case Report Form.

##### **9.4.3.1 Relationship to the Study Drug**

The event's relationship to the Study Drug (olezarsen or placebo) is characterized by 1 of the following:

- **Related:** There is clear evidence that the event is related to the use of Study Drug, e.g., confirmation by positive re-challenge test
- **Possible:** The event cannot be explained by the patient's medical condition, concomitant therapy, or other causes, and there is a plausible temporal relationship between the event and Study Drug (olezarsen or placebo) administration
- **Unlikely/Remote:** An event for which an alternative explanation is more likely (e.g., concomitant medications or ongoing medical conditions) or the temporal relationship to Study Drug (ISIS 678354 or placebo) administration and/or exposure suggests that a causal relationship is unlikely (For reporting purposes, Unlikely/Remote will be grouped together with Not Related)
- **Not Related:** The event can be readily explained by the patient's underlying medical condition, concomitant therapy, or other causes, and therefore, the Investigator believes no relationship exists between the event and Study Drug

#### 9.4.3.2 Severity

The severity of AEs and SAEs relating to laboratory tests will be graded based on criteria from the CTCAE Version 5.0, November 2017 (refer to [Appendix D](#)). Any AE not listed in [Appendix D](#) will be graded as follows:

- **Mild:** The event is easily tolerated by the patient and does not affect the patient's usual daily activities
- **Moderate:** The event causes the patient more discomfort and interrupts the patient's usual daily activities
- **Severe:** The event is incapacitating and causes considerable interference with the patient's usual daily activities

The severity of AEs and SAEs relating to AEs at the injection site will be graded based on criteria from the Toxicity Grading Scale for Healthy Adult and Adolescent Volunteers Enrolled in Preventive Vaccine Clinical Trials, Sept 2007 (refer to [Appendix D](#)).

If the event is an SAE, then all applicable seriousness criteria must be indicated (criteria listed in Section [9.3.3](#)).

#### 9.4.3.3 Action Taken with Study Drug

Action taken with Study Drug (olezarsen or placebo) due to the event is characterized by 1 of the following.

- **None:** No changes were made to Study Drug (olezarsen or placebo) administration and dose
- **Not Applicable:** SAE/AE was reported during Screening Period prior to Study Drug administration
- **Permanently Discontinued:** Study Drug was discontinued and not restarted
- **Temporarily Interrupted, Restarted - Same Dose:** Dosing and/or dosing frequency was temporarily interrupted/changed or delayed due to the AE and restarted at the same dose
- **Reduced Dose:** Dosing was reduced to a lower dose

#### 9.4.3.4 Treatment Given for Adverse Event

Any treatment (e.g., medications or procedures) given for the AE should be recorded on the Adverse Event Case Report Form. Treatment should also be recorded on the concomitant treatment or ancillary procedures eCRF, as appropriate.

#### 9.4.3.5 Outcome of the Adverse Event

If the event is a non-serious AE, then the event's outcome is characterized by 1 of the following:

- **AE Persists:** Patient terminates from the trial and the AE continues
- **Recovered:** Patient recovered completely from the AE

- **Became Serious:** The event became serious (the date that the event became serious should be recorded as the Resolution Date of that AE and the Onset Date of the corresponding SAE)
- **Change in Severity (if applicable):** AE severity changed

If the event is an SAE, then the event's outcome is characterized by 1 of the following:

- **Ongoing:** SAE continuing
- **Persists (as non-serious AE):** Patient has not fully recovered but the event no longer meets serious criteria and should be captured as an AE on the non-serious AE eCRF (the SAE resolution date should be entered as the date of onset of that AE)
- **Recovered:** Patient recovered completely from the SAE (the date of recovery should be entered as the SAE resolution date)
- **Recovered with Sequelae:** The signs/symptoms of the reported SAE have improved but not completely resolved, and a new baseline for the patient is established since full recovery is not expected
- **Fatal:** Patient died (the date of death should be entered as the SAE resolution date)
- **Unknown:** The outcome of the reported SAE is not available, e.g., patient is lost to follow-up

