#### 4.10.2 Adverse Events

##### 4.10.2.1 Definition of Treatment-Emergent Adverse Event (TEAE)

TEAEs are defined as adverse events that occurred on or after the first administration of Study Drug or worsened relative to the pre-treatment state. Note that imputed dates will be used for defining TEAEs.

In addition, if severity of an AE changes during the study, a separate AE will be recorded for each severity on the AE CRF. The “first” and “second” AEs will be defined based on AE start date, and AE start date of the second record will be the same as AE stop date of the first record. AE severity (mild/moderate/severe) should be compared pairwise between these linked events when defining TEAEs. Consider 2 cases below:

Case 1: The first AE record in the pair occurs before first dosing, and the second AE record occurs after first dosing.

If the AE severity of the second record is worse than that of the first record, then only the second AE is deemed as a TEAE. Otherwise, neither record is considered as TEAE.

Case 2: Both AE records in the pair occur after first dosing.

The worst AE will be deemed as a TEAE.

All TEAEs identified based on the rules above will be summarized in the event number analysis.

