##### 4.10.2.2 Analysis for TEAEs

All AEs will be coded to SOC and PT using the MedDRA. The final MedDRA version used will be designated in the clinical study report. The frequency and incidence of AEs will be summarized by SOC and PT. The SOC's will be presented in alphabetical order, and the PTs will be presented in descending frequency order within each SOC. Subjects reporting more than one AEs will be counted only once for each level of summation (most severe incident for the severity tables and most related incidence for the relationship tables).

The frequency of patients with any incidences of AEs and the number of events will be presented by treatment group and total olezarsen treated for the following summaries:

- Any TEAEs by SOC and PT
- Any TEAEs by PT
- TEAEs related to Study Drug by SOC and PT. Related is defined as “Related”, “Possible”, or missing relationship to Study Drug

- Any TEAEs by maximum severity, SOC and PT. At each severity level of subject summarization, a subject is classified according to the highest reported severity if the subject reported one or more events. TEAEs with missing severity will be categorized as "Missing" for this summary.
- TEAEs related to Study Drug by severity, SOC, and PT
- Serious TEAEs by SOC and PT
- Serious TEAEs related to Study Drug by SOC and PT
- Serious TEAEs related to Study Drug by SOC and PT
- Serious TEAEs by severity
- Serious TEAEs related to study drug by severity
- TEAEs leading to permanent Study Drug discontinuation by SOC and PT
- TEAEs related to Study Drug leading to permanent Study Drug discontinuation by SOC and PT
- TEAEs leading to death by SOC and PT
- TEAE with an incidence rate > 5% in any treatment group by PT
- Non-serious TEAE with an incidence rate > 5% in any treatment group by PT

An overall summary of frequency and incidence of AEs of above unique categories will be provided by treatment group and total olezarsen treated. By-subject listing of all AEs will be provided, in which non-treatment emergent AEs will be included and be noted. The following additional listings will be provided for TEAEs unless otherwise specified.

- Listing of treatment-emergent SAEs
- Listing of TEAEs related to study drug
- Listing of TEAEs leading to discontinuation of Study Drug
- Listing of all deaths

To define TEAEs, the algorithm in Section 4.10.2.3 will be applied to impute missing or partial start date or end date. Original reported dates will be used for listings.

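### SAP 4.10.2.1 links split adverse event records only when severity changes, so an event whose seriousness changes at constant severity is counted two or three times in the event numbers

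*Combined protocol and SAP*

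**What the plan says.** Protocol 9.4.3.5 splits a continuing event in two situations. When a non-serious AE turns into an SAE, "the date that the event became serious should be recorded as the Resolution Date of that AE and the Onset Date of the corresponding SAE". When an SAE no longer meets the seriousness criteria but has not resolved, "the SAE resolution date should be entered as the date of onset of that AE". Protocol 9.3.3 asks for severity and seriousness to be judged separately, and Protocol 9.4.1 collects SAEs from consent onward.

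SAP 4.10.2.1 starts from an onset-date test: "TEAEs are defined as adverse events that occurred on or after the first administration of Study Drug or worsened relative to the pre-treatment state". It then gives a linking rule for one kind of split: "if severity of an AE changes during the study, a separate AE will be recorded for each severity on the AE CRF". The linked records are contiguous, in that "AE start date of the second record will be the same as AE stop date of the first record", and their severity grades "should be compared pairwise between these linked events when defining TEAEs". If the pair straddles first dose, the second record is a TEAE only if it is more severe; otherwise neither record is. If both records are post-dose, "The worst AE will be deemed as a TEAE". Every TEAE found this way goes into the event-number analysis. The rule does not mention seriousness.

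SAP 4.10.2.2 shows numbers of events beside numbers of patients, counts each subject once per level of summary, and lists among its tables "Non-serious TEAE with an incidence rate > 5% in any treatment group by PT".

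Protocol 10.6.2 defines a TEAE by presence rather than record date: the event must be absent before Study Drug, or must worsen after it starts. SAP 4.13 lists no change to that definition.

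**The concern.** The SAP accepts that a continuation record is not a new event. For severity splits it keeps one of two post-dose records, and it refuses to call an improving pre-dose event treatment-emergent. Protocol 9.4.3.5 creates a second kind of split, with the same contiguous dates, and no rule in the SAP joins those records. Because seriousness can change while severity does not, some split events fall outside the link.

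Three outputs are exposed: the event-number columns, the non-serious TEAE table (which can receive the tail of an SAE), and the TEAE classification of an SAE that began in screening and was improving. In the last case, recovery from a pre-treatment event would be reported as an adverse event arising on treatment.

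**Working it through.** The plan states no figure on this point, so there is nothing to reproduce. The check applies the SAP 4.10.2.1 rules to constructed record sequences and compares them with a rule that links every continuation record and treats becoming serious as worsening.

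**Step 1. Count for a post-dose event.** Let k be the number of changes of seriousness at which severity does not change. Each such change breaks the chain, and a linked chain yields one TEAE, so the number of TEAEs is 1 + k.

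**Step 2. Cases.**

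| Sequence | SAP as written | Seriousness also linked |
|---|---|---|
| Post-dose AE to SAE, same severity (k = 1) | 2 TEAEs: 1 serious, 1 non-serious | 1 serious |
| Post-dose AE to SAE to AE, same severity (k = 2) | 3 TEAEs: 1 serious, 2 non-serious | 1 serious |
| Post-dose moderate AE, severe SAE, mild AE (k = 0) | 1 serious | 1 serious |
| Screening SAE, still serious at first dose, non-serious on Day 5, same severity | 1 non-serious TEAE | 0 |
| As above, but severity falls at the change | 0 | 0 |
| Screening SAE that becomes non-serious before Day 1 | 0 | 0 |

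In the fourth row the continuation record has a post-dose onset and passes the SAP date test. The event was present before dosing and did not worsen, so it fails Protocol 10.6.2. There is one further route: SAP 4.10.2.3 moves a start date with a missing day in the month of first dose to the day of first dose, so a downgrade shortly before dosing could be dated to Day 1.

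**Step 3. Non-serious table.** The design gives 152/2 = 76 patients per cohort, hence 76 × 3/4 = 57 in each olezarsen group and 2 × 76 × 1/4 = 38 on pooled placebo. The table takes preferred terms above 5% in any group:

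- Olezarsen group: 2/57 = 3.5%, 3/57 = 5.3%, so at least 3 patients are needed.
- Pooled placebo: 1/38 = 2.6%, 2/38 = 5.3%, so at least 2 patients are needed.

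A single SAE tail in an uncommon term does not appear. A tail matters if the term is already listed, or if that patient takes it across the threshold.

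**Step 4. Outputs that do not move for a post-dose split.**

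- Patient incidence for all TEAEs by SOC and PT: each subject counts once per level (SAP 4.10.2.2).
- Crude risk differences and exposure-adjusted incidence: both use patients with at least one event, and the latter uses time to the first event (SAP 4.2.1).
- Time to onset: it is summarised for the first event, which carries the true onset date (SAP 4.10.2.5).
- Efficacy: the record-splitting rule does not enter it.

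**The case against.** The strongest reply is that little of consequence depends on this. The between-group safety comparisons rest on patients, not records. The exposure-adjusted event rate does count events, but the SAP calls for it only for AEs of special interest (4.10.2.4), which are reviewed individually, and for MACE (4.11.3.1), which is adjudicated. The recording rule is the same in every blinded arm. All of this stands, and it limits the point mainly to descriptive event numbers.

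The screening case is also a corner case. It needs a patient dosed while an SAE still meets a seriousness criterion, despite the eligibility checks, followed by a downgrade at unchanged severity. It is fair to add that Protocol 10.6.2 would exclude this event and that SAP 4.13 declares no departure. But the SAP's operative test is the record's onset date, so a programmer following the SAP would include it.

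The data system may link these records in a way the documents do not show, or programmers may link on contiguous dates alone. The SAP does not say so, and date linking alone would not be safe. At equal severity the worst record is undefined, and a screening AE that becomes serious after dosing at unchanged severity would drop out, because only severity is compared.

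A reader might also infer that times to onset and durations are wrong in general. The documents do not support that. Time to onset uses the first event, and AE duration is summarised only for injection-site events, where SAP 4.10.2.5.6 and 4.10.2.5.7 have their own rules for several records from one injection.

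**Conclusion.** The gap is real and minor. At unchanged severity, one post-dose event is counted as 2 or 3 TEAEs in the event-number columns. Its non-serious tail can add the patient to the non-serious table if the term exceeds 5%. A screening SAE downgraded after first dose at the same severity becomes a TEAE against Protocol 10.6.2, and that patient would then be wrongly counted at patient level too.

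Two broader readings should be resisted. Split events are not always counted more than once: a severity change at the same time triggers the existing link and the count is 1. Nor can a trial-wide excess be stated, since the documents do not say how many SAEs will have a non-serious lead-in or tail, or how many of those will keep the same severity. The conclusion assumes that the SAP is programmed as written and that no linkage exists outside the documents.

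**What to change.** Extend the linkage in SAP 4.10.2.1 to changes of seriousness:

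- Contiguous records of the same event count as one event, with first onset, last resolution, worst severity, and serious if ever serious.
- The event is treatment-emergent if it started on or after first dose, or if after first dose its severity increased or it became serious.
- A pre-dose event that only improves or becomes non-serious is not a TEAE.
- A pre-dose AE that becomes serious after first dose stays in the serious TEAE tables, with the date it became serious as its treatment-emergent onset. Without this line the linkage could remove a genuine serious TEAE.
- State that the SAP definition of a TEAE follows Protocol 10.6.2.

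The cost is a few lines of SAP text and programming. The dates and outcome codes required by Protocol 9.4.3.5 are already collected.

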#### 9.4.3.6 Follow-up of Adverse Event

##### Investigator Follow-Up

During the Study Period, the Investigator should follow each AE until the event has resolved to baseline grade or better, the event is assessed as stable, the patient is lost to follow-up, or the patient withdraws consent. Every effort should be made to follow all SAEs considered to be related to Study Drug or related to study procedures until a final outcome can be reported.

Resolution of AE (with dates) should be documented on the Adverse Event eCRF and in the patient's medical record to facilitate source data verification.

Investigator should follow-up or support the Sponsor's effort to follow up with all pregnancies reported during the study from either the study patient or the female partner of male study patient until pregnancy outcome is available.

##### Sponsor Follow-Up

For SAEs, AESI and pregnancy cases in patients who have completed or terminated the study, the Sponsor or a designee should follow-up by telephone, fax, email, and/or a monitoring visit (on-site or remote access) to obtain additional case details and outcome information (e.g., from hospital discharge summaries, consultant reports, autopsy reports) in order to perform an independent medical assessment of the reported case.

#### 9.4.3.7 Adjudication Committees

All AEs and SAEs that occur during the study that are consistent with MACE will be adjudicated by a blinded, independent MACE-Adjudication Committee (MACE-AC) as outlined in the MACE Adjudication Charter.

MACE-AC will adjudicate all fatal events and events suggestive of non-fatal myocardial infarction, hospitalization for unstable angina, hospitalization for (worsening) heart failure, coronary and non-coronary revascularization procedures, and stroke. The criteria used by the MACE-AC to determine the occurrence of any of the events will follow the recommendations included in published Cardiovascular and Stroke Endpoint Definitions for Clinical Trials ([Hicks et al. 2018](#); [Thygesen et al. 2018](#)).

All AEs and SAEs that occur during the study that are consistent with an event of acute pancreatitis will be adjudicated by a blinded, independent committee according to the Atlanta classification of acute pancreatitis ([Banks et al. 2013](#)) and as outlined in the Pancreatitis Adjudication Charter. In addition, data for episodes of acute pancreatitis or suspected pancreatitis in the 5 years prior to enrollment will be collected by review of each patient's medical chart and these events will also be adjudicated.

## 9.5 Procedures for Handling Special Situations

### 9.5.1 Abnormalities of Laboratory Tests

Clinically significant abnormal laboratory test results may, in the opinion of the Investigator, constitute or be associated with an AE. Examples of these include abnormal laboratory results that are associated with symptoms, or require treatment, e.g., bleeding due to thrombocytopenia, tetany due to hypocalcemia, or cardiac arrhythmias due to hyperkalemia. Whenever possible, the underlying diagnosis should be listed in preference to abnormal laboratory values as AEs. Clinically significant abnormalities will be monitored by the Investigator until the parameter returns to its baseline value or until agreement is reached between the Investigator and Sponsor Medical Monitor. Laboratory abnormalities deemed not clinically significant (NCS) by the Investigator should not be reported as AEs. Similarly, laboratory abnormalities reported as AEs by the Investigator should not be deemed NCS on the laboratory sheet.

The Investigator is responsible for reviewing and signing all laboratory reports. The signed clinical laboratory reports will serve as source documents and should include the Investigator's assessment of clinical significance of out of range/abnormal laboratory values.

### 9.5.2 Prescheduled or Elective Procedures or Routinely Scheduled Treatments

A prescheduled or elective procedure or a routinely scheduled treatment will not be considered an SAE, even if the patient is hospitalized; the Study Center must document all of the following:

- The prescheduled or elective procedure or routinely scheduled treatment was scheduled (or was on a waiting list to be scheduled) prior to obtaining the patient's consent to participate in the study
- The condition that required the prescheduled or elective procedure or routinely scheduled treatment was present before and did not worsen or progress in the opinion of the Investigator between the patient's consent to participate in the study and the timing of the procedure or treatment
- The prescheduled or elective procedure or routinely scheduled treatment is the sole reason for the intervention or hospital admission

### 9.5.3 Dosing Errors

Study Drug (olezarsen or placebo) errors (for example, overdose, underdose, and administration error) should be reported as a medication error on the Protocol Deviation CRF and an AE CRF, if applicable. A brief description should be provided when reporting the deviation, including whether the patient was symptomatic (list symptoms) or asymptomatic, and whether the event was accidental or intentional.

Dosing details should also be captured on the Dosing Case Report Form. If the patient takes a dose of Study Drug that exceeds protocol specifications and the patient is symptomatic, then each symptom should be documented as an AE and be reported per Section 9.4.

An overdose is the accidental or intentional use of a drug in an amount higher than the dose being studied. An overdose or incorrect administration of study treatment is not itself an adverse event, but it may result in an adverse event. All adverse events associated with an overdose or incorrect administration of Study Drug should be recorded on the Adverse Event eCRF. The event should be reported to the Sponsor immediately (i.e., no more than 24 hours after learning of the event).

**Should an overdose occur**, the Investigator or designee should refer to the Guidance to Investigator's section of the Investigator's Brochure and contact the Sponsor or designee within 24 hours.

### 9.5.4 Contraception and Pregnancy

Male patients and female patients of childbearing potential must continue to use appropriate contraception with their partners, or refrain from sexual activity, as described in Section 6.3.1.

If a patient becomes pregnant or a pregnancy is suspected, or if a male patient makes or believes that he has made someone pregnant during the study, or within 30 weeks of the last dose of study drug, then the Study Center staff must be informed immediately. An Initial Pregnancy Form should be submitted to the Sponsor or designee **within 24 hours** of first learning of the occurrence of pregnancy. Follow-up information including delivery or termination is reported by designating as 'Follow-up' on the Pregnancy Forms and reported within 24 hours of awareness of the pregnancy outcome.

Payment for all aspects of obstetrical care, child or related care will be the patient's responsibility.

Female patients: If a suspected pregnancy occurs while on the study (including during the Follow-up Period), a pregnancy test will be performed. The patient with a confirmed pregnancy will be immediately withdrawn from treatment with Study Drug. However, the patient will be encouraged to complete the post-treatment follow-up portion of the study to the extent that study procedures do not interfere with the pregnancy. Regardless of continued study participation, the Investigator will assist the patient in getting obstetrical care and the progress of the pregnancy will be followed until the outcome of the pregnancy is known (i.e., delivery, elective termination, or spontaneous abortion). If the pregnancy results in the birth of a child, the Study Center and Sponsor may require access to the mother and infant's medical records to obtain additional information relevant to the pregnancy progress and outcome. A longer follow-up may be required if the newborn child experiences a medical condition. Follow-up will be performed to

the extent permitted by the applicable regulations and privacy considerations, e.g., pregnancy ICF may be required.

Male patients: The progress of the pregnancy of a male patient's partner should be followed until the outcome of the pregnancy is known (i.e., delivery, elective termination, or spontaneous abortion). If the pregnancy results in the birth of a child, the Study Center and Sponsor may follow-up with the mother and may request access to the mother and infant's medical records to obtain additional information relevant to the pregnancy progress and outcome. A longer follow-up may be required if the newborn child experiences a medical condition. Follow-up will be performed to the extent permitted by the applicable regulations and privacy considerations, e.g., partner ICF may be required.

Spontaneous abortion/miscarriage is to be reported as an SAE. See Section 9.4.1 for additional information regarding SAE reporting.

